9.10 Interval Evaluation

At any point following the venous stenting procedure, the patient may present with symptoms of clinically significant obstruction of the target vessel. Patients with possible obstruction should undergo all medical examinations and interventions as deemed appropriate for medical care. All technical examinations (DUS, IVUS, or venograms) obtained during the course of the evaluation will be submitted as part of the case report form and will be submitted to the Core Laboratory for determination of primary endpoint.

Patients who undergo re-intervention, but who are found on Core Laboratory assessment to have vessel patency prior to the re-intervention will not be counted as a primary efficacy endpoint failure. Patients who undergo an interval evaluation but do not receive an intervention will have their status (patency/non-patency) determined by the Core Laboratory. Patients who are found to be patent by Core Laboratory analysis will continue in the study through 12 months.

Patients who undergo another intervention at any time prior to the 12 month evaluation, or who are found to have in-stent stenosis > 50%, by Core Laboratory assessment, will be considered to have failed the primary efficacy endpoint and will not be required to have further assessment of vessel patency or other secondary endpoints.

All patients will complete the 30-day safety assessment regardless of primary patency status.

9.11 24 Month Evaluation (730 days ± 90 days)

- Telephone follow-up for SAE assessment. May be performed in-person, at the discretion of the investigator.
- Duplex ultrasound to assess vessel patency. (Office or laboratory visit)

9.12 36 Month Evaluation (1,095 days ± 90 days)

- Telephone follow-up for SAE assessment. May be performed in-person, at the discretion of the investigator.
- Duplex ultrasound to assess vessel patency. (Office or laboratory visit)

STE-HUM-007P US Clinical Protocol Revision C

Confidential

Page 31 of 70

9.13 48 Month Evaluation (1,460 days ± 90 days)

• Telephone follow-up for SAE assessment. May be performed in-person, at the discretion of the investigator.

9.14 60 Month Evaluation (1,825 days ± 90 days)

• Telephone follow-up for SAE assessment. May be performed in-person, at the discretion of the investigator.

STE-HUM-007P US Clinical Protocol Revision C

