Reference Vein Diameter (RVD)	Reference Vein Diameter (RVD) is defined as the normal diameter of the target vessel (CIV, EIV, or CFV)
Procedural technical success	Achievement of a final residual target vessel diameter stenosis of ≤50% as measured on the post procedural venogram, without skipped lesion regions, with placement of the study device alone with or without post-stenting balloon dilation as needed
POST-PROCEDURAL DEFINITION	DNS
Term	Definition
Device or procedure related death	Death specifically attributable to the Veniti Vici Venous Stent System or the stent placement procedure
Late technical success	 Absence of device movement >10mm related to anatomical landmarks or any migration leading to symptoms or requiring therapy
	 Absence of stent occlusion by thrombosis or restenosis, defined as reduction in treated segment lumen more than 50% from the post-procedure vessel lumen diameter as measured by post-procedural venogram or DUS
	 Structural integrity, defined as the absence of pinching (focal compression), recoil (poor radial resistive force) or kinking (stent bending upon itself) that results in >50% diameter reduction of the stent, or fracture
Patency (Primary Endpoint)	At 12 months post-intervention, freedom from occlusion by thrombosis AND freedom from surgical or endovascular intervention on target vessel with re-stenosis or stent occlusion to maintain patency AND freedom from in stent diameter stenosis more than 50% as measured by venogram. For patients refusing the venographic assessment at 12 months, DUS-determined patency will be used instead

Rate of intervention lesion (RIL)	Re-intervention within the target vessel with in-stent stenosis or thrombosis to achieve patency (constitutes failure on the primary endpoint)
Rate of intervention of extremity (RIE)	Re-intervention of a non-target lesion venous segment of the ipsilateral (target) extremity required to maintain ipsilateral extremity venous outflow (does NOT constitute failure of the primary endpoint)
In-stent stenosis (primary endpoint)	Non-occlusive reduction in the treated segment lumen diameter more than 50% from the post-procedural vessel lumen diameter per venogram or DUS
In-stent thrombosis (primary endpoint)	Occlusion of the stented target vessel due to thrombosis; early thrombosis is that which occurs ≤30 days; late thrombosis is that which occurs >30 days

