	The follow-up period is 60 months.						
Follow-Up	The 12-month data from at least 156 patients will be submitted to FDA to support a Pre-Market Approval (PMA) application.						
Primary Efficacy Endpoint	The primary efficacy endpoint for this study will be the primary patency rate at 12 months post-intervention, defined as freedom from occlusion by thrombosis AND freedom from surgical or endovascular intervention on target vessel which are found to have re-stenosis or stent occlusion to maintain patency AND freedom from in-stent stenosis more than 50% by venogram. For patients refusing the venographic assessment at 12 months, DUS-determined patency will be used instead.						
Primary Safety	The primary safety endpoint for this study will be a composite endpoint of any major adverse event within 30 days, as adjudicated						

Page 14 of 70

Endpoint	by a Clinical Events Committee. Major Adverse Events are listed in Section 11.1.4.							
Secondary Efficacy Endpoint	The formal secondary endpoint for this study will be a binary response variable based on an improvement in VCSS by at least 50% at 12 months post-intervention.							
	 Procedural Endpoints Procedural technical success, defined as achievement of a final residual diameter stenosis of ≤50% as measured by venogram without skipped lesion areas with placement of the study device alone with or without post-stenting balloon dilation 							
Ancillary Analyses	 Lesion success defined as achievement of ≤50% residual diameter stenosis using any percutaneous method (including use of non- study devices) 							
	• Procedural success defined as procedural technical success without the occurrence of major adverse event between the index procedure and discharge							

	Late technical success (through 12 months) defined as:					
	Absence of migration					
	Absence of stent embolization					
Ancillary Analyses (continued)	Achievement of primary patency					
	Structural integrity, defined as the absence of:					
	 Pinching, defined as focal compression of the stent with > 50% diameter reduction of the stent 					
	 Kinking, defined as >50% diameter reduction of the stent with the stent doubling or bending on itself 					
	 Recoil, defined a poor radial resistance to diffuse collapse, which results in >50% diameter reduction of the stent (i.e., stent diameters obtained throughout the study period as compared to the final stent diameter after insertion measured by DUS or venogram). Fracture(s) 					

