7 STUDY OBJECTIVE AND DESIGN

The VIRTUS trial is a prospective, multicenter, single arm, non-randomized study to define safety and efficacy of the Veniti Vici Venous Stent System in relation to predefined Objective Performance goals. The objective of this study is to assess the safety and efficacy of the Veniti Vici Venous Stent System in achieving patency of the target venous lesion in patients who present with clinically significant chronic non-malignant occlusion of the iliofemoral venous outflow tract.

7.1 **Primary Endpoint – Efficacy:**

The primary efficacy endpoint for this study will be the primary patency rate at 12 months post-intervention, defined as freedom from occlusion by thrombosis AND freedom from surgical or endovascular intervention on target vessel which are found to have re-stenosis or stent occlusion to maintain patency AND freedom from in-stent stenosis more than 50% by venogram. For patients refusing the venographic assessment at 12 months, DUS-determined patency will be used instead.

7.2 Primary Endpoint – Safety:

The primary safety endpoint for this study will be a composite endpoint of any Major Adverse Event within 30 days, as adjudicated by a Clinical Events Committee. Major Adverse Events are listed in Section 11.1.4.

7.3 Secondary Endpoint – Efficacy:

The formal secondary endpoint of this study is a binary response variable based on whether or not a subject achieves at least 50% improvement on the Venous Clinical Severity Scoring (VCSS) scale at 12 months post-intervention.

7.4 Ancillary Outcomes:

Procedural Endpoints

- Procedural technical success, defined as achievement of a final residual target vessel diameter stenosis of ≤50% as measured on the postprocedural venogram, without skipped lesion regions, with placement of the study device alone with or without post-stenting balloon dilation as needed
- 2. Lesion success defined as achievement of ≤50% residual diameter stenosis using any percutaneous method (including the use of non-study devices)
- 3. Procedural success defined as procedural technical success without the occurrence of major adverse event between the index procedure and discharge
- 4. Late technical success (through 12 months) defined as:
 - a. Absence of migration
 - b. Absence of stent embolization
 - c. Achievement of primary patency
 - d. Structural integrity, defined as the absence of:
 - i. Pinching, defined as focal compression of the stent with > 50% diameter reduction of the stent

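### Section 15.8.1 fails any re-intervention in the stented area, while the endpoint definition and Section 9.10 (second paragraph) excuse one on a patent stent

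*Combined protocol and SAP*

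**What the plan says.** **Conditional rule.** Section 1 defines primary patency to include "freedom from surgical or endovascular intervention on target vessel with re-stenosis or stent occlusion to maintain patency". Its entry for the rate of intervention lesion reads "Re-intervention within the target vessel with in-stent stenosis or thrombosis to achieve patency (constitutes failure on the primary endpoint". The synopsis and Section 7.1 require "freedom from surgical or endovascular intervention on target vessel which are found to have re-stenosis or stent occlusion to maintain patency". Section 9.10, second paragraph, applies the condition to the exact case: patients who are re-intervened but found on Core Laboratory assessment "to have vessel patency prior to the re-intervention will not be counted as a primary efficacy endpoint failure".

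**Unconditional rule.** Section 15.8.1 lists three patency failure events: thrombosis, re-intervention and restenosis above 50% on imaging. The re-intervention item requires only that the stented area be involved. Section 9.10, third paragraph, says that "Patients who undergo another intervention at any time prior to the 12 month evaluation", or who are found to have in-stent stenosis above 50% by the Core Laboratory, have failed. It then releases them from further patency assessment.

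**Follow-up of excused patients.** The second paragraph of 9.10 also says: "Patients who are found to be patent by Core Laboratory analysis will continue in the study through 12 months". That sentence comes directly after one about patients evaluated without an intervention. Section 15.8.1 scores success on the 12-month image, provided no earlier study showed more than 50% restenosis. It does not say whether an image taken after a re-intervention qualifies.

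**The concern.** Section 15.8.1 is the text a programmer will follow. Applied as written, it gives a different primary result from the endpoint defined in Sections 1, 2 and 7.1 whenever a patient is re-intervened on a stent that the Core Laboratory reads as patent.

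The trial is single-arm and its result is compared with fixed goals. If the rule is chosen after outcomes are visible, whoever chooses can see which choice meets the goal.

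There is also a data-collection consequence. A site that follows the third paragraph of 9.10 may regard a re-intervened patient as failed and obtain no 12-month image. If the conditional rule is applied later, that patient has neither a failure event nor an image. Section 15.8.1 would then drop the patient from the per-protocol analysis and count a failure in the worst-case analysis. Depending on the paragraph followed, the same patient could be a failure, be left out or, with a clear later image, be a success.

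**Working it through.** **1. The passages side by side, for a patient re-intervened on a stent the Core Laboratory reads as patent**

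| Place | Condition on the re-intervention | Status |
|---|---|---|
| Section 1, Patency | re-stenosis or occlusion | not a failure |
| Section 1, rate of intervention lesion | in-stent stenosis or thrombosis | not a failure |
| Synopsis and 7.1 | re-stenosis or occlusion | not a failure |
| 9.10, second paragraph | Core Laboratory reads the vessel as not patent | not a failure |
| 9.10, third paragraph, literal reading | none | failure |
| 15.8.1, failure list | none | failure |

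**2. Inputs**
- Goals: NT 0.855, PT 0.679. Design rates: NT 0.955, PT 0.779. One-sided level 0.025. Evaluable N 156 (Section 15.7).
- Weights: NT 0.26, PT 0.74 (15.7 and 15.8.1; 15.8.1 also prints 0.266 once, and 0.26 is used here).
- Split of the 156 (assumption): 15.1 plans 45 NT and 125 PT of 170, so 156 × 45/170 = 41.3 and 156 × 125/170 = 114.7, taken as 41 NT and 115 PT.

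**3. The plan's own power**
- Null SE = √(0.26² × 0.855 × 0.145/41 + 0.74² × 0.679 × 0.321/115) = √(0.0002044 + 0.0010379) = 0.03525.
- SE at the design rates = √(0.26² × 0.955 × 0.045/41 + 0.74² × 0.779 × 0.221/115) = 0.02984.
- Power ≈ Φ[(0.10 − 1.96 × 0.03525)/0.02984] = Φ(1.04) = 85.0%.
- Exact binomial enumeration gives 86.1%, 87.0% and 83.2% at NT/PT splits of 40/116, 41/115 and 42/114 (mean 85.4%).
- Section 15.7 states a target of at least 85% and an estimate of 84%. These are reproduced to within the effect of the split.

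**4. Effect of one reclassified patient on Z**
- PT: (0.74/115)/0.03525 = 0.183. NT: (0.26/41)/0.03525 = 0.180.
- Expected Z at the design rates = 0.10/0.03525 = 2.84. Margin over 1.96 in PT patients: (2.84 − 1.96)/0.183 = 4.8.

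**5. Assumed data sets, NT 39/41 throughout**

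| PT successes of 115 | Z | one-sided p | Z-test |
|---|---|---|---|
| 90 | 2.885 | 0.0020 | met |
| 87 | 2.337 | 0.0097 | met |
| 85 | 1.972 | 0.0243 | met |
| 84 | 1.790 | 0.0368 | not met |

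The result is lost at 84. That is six moves from 90, three from 87 and one from 85. Observed rates stay above both goals in every row (NT 39/41 = 0.951; PT at lowest 84/115 = 0.730), so the additional observed-rate conditions in 15.7 do not decide these cases.

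**6. Illustration of power**

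Assume that the design rates hold under the conditional rule, and that 1%, 2% or 3% of each stratum would be rescored as failures under the unconditional rule. Exact enumeration, averaged over the three splits and including the observed-rate conditions of 15.7, gives 85% with none rescored, then 75%, 64% and 51%.

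**The case against.** **The intended rule can be inferred.** Section 1 (twice), the synopsis, 7.1 and the second paragraph of 9.10 all carry the condition. The third paragraph of 9.10 can be reconciled with them if its reference to Core Laboratory assessment qualifies the intervention as well as the stenosis. This stands, and it points to the shorter repair. It does not remove the conflict, because the 15.8.1 item has no such qualifier.

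**Section 15.8.1 gives one answer.** A reader might infer that a re-intervened patient with a clear 12-month image meets both statuses in 15.8.1 with no way to choose. The documents do not firmly support that. The endpoint joins freedom-from components, so any listed failure event can be read as defeating success. The sentence on continuing to 12 months may also cover only patients without an intervention. On that reading 15.8.1 is consistent with itself, but it still contradicts the endpoint definition and the second paragraph of 9.10.

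**The size is hypothetical.** Correct. The documents give no frequency of re-intervention on patent stents. Near the design rates a few such patients would not change the conclusion, and the three-patient and one-patient reversals use deliberately closer results.

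**The literature rates point to one rule.** Section 15.5.2 describes them as free of re-intervention with no condition. Yet in the rows where stenosis and occlusion are both filled in, patency is their exact complement: NT 143 − 1 − 2 = 140; NT 100 − 1 − 6 = 93%; PT, before the 3% adjustment for silent restenosis, 100 − 3 − 17 = 80%. That is compatible with the conditional rule but does not prove it.

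**Imaging modality.** A reader might infer that the place of IVUS in the endpoint is undefined. Section 1 largely answers this by defining in-stent stenosis for the primary endpoint by venogram or duplex ultrasound. Sections 7.1, 9.6 and 9.9 give the order between those two.

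**Conclusion.** The contradiction is in the current text and must be resolved before analysis. Section 15.8.1, and the third paragraph of 9.10 read literally, fail a patient whom Section 1, the synopsis, 7.1 and the second paragraph of 9.10 do not. Whether an image after an excused re-intervention can establish 12-month primary patency is not stated.

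The effect is about 0.18 in Z per patient, assuming a 41/115 split. That is enough to decide a close result and unlikely to overturn one at the design rates unless about six PT patients are affected. The power figures rest on an assumed 1% to 3% and are illustration only.

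A reader might go further and infer that the sample size or power is wrong, or that the type I error is inflated. Neither follows. The plan's power reproduces, and the excusing rule would produce false positives only if 15.8.1 were the intended endpoint, which is the reading with less support in the text.

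**What to change.** Before endpoint data are reviewed:

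1. Put one rule in every place. The shortest edit adds the condition (re-stenosis or stent occlusion, as read by the Core Laboratory) to the re-intervention item in 15.8.1 and to the third paragraph of 9.10. If the sponsor intends the unconditional rule, edit Section 1, the synopsis, 7.1 and the second paragraph of 9.10 instead.
2. State that this rule decides the analysed status.
3. State whether imaging after an excused re-intervention counts towards 12-month primary patency, and make clear in 9.10 whether such patients continue to the 12-month assessment.
4. Pre-specify the other rule as a sensitivity analysis.
5. Optionally, add a cross-reference from 15.8.1 to the Section 1 definition of in-stent stenosis and to the venogram-first, duplex-on-refusal order in 7.1, 9.6 and 9.9.

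The cost is wording changes and one extra run on data already collected; sample size, significance level and visit schedule are unchanged. The downside is that, under the unconditional rule, the reported patency rate and the power may be lower.

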9.6 Discharge or Three Days Post-Procedure (whichever comes first)

- Duplex ultrasound to determine post-procedural target vessel lumen diameter (For patients refusing the venographic assessment at 12 months [or prior Interval Evaluation, as applicable], DUS-determined patency will be used instead, with the DUS obtained at the Discharge or Three Days Post-Procedure visit serving as the baseline).
- Determination of discharge
- Anticoagulation Review, based on the Extended Anticoagulation Protocol (See Appendix 2.)
- Adverse event assessment
- Patients who do not meet intra-procedural inclusion criteria (and who do not receive the implanted study device) should be followed only through hospital discharge for protocol deviations and adverse events. This visit will conclude participation for these screen failed patients. These subjects will not be included in the statistical analysis.

9.7 1 Month Evaluation (30 days -7/+14 days)

- Physical examination (to assess for the presence of Adverse Events)
- Anticoagulation Review, based on the Extended Anticoagulation Protocol (See Appendix 2.)

9.8 6 Month Evaluation (180 days ± 30 days)

- Physical examination (to assess for the presence of Adverse Events)
- Duplex ultrasound (required only for first 30 patients to assess patency)
- CIVIQ-2 Quality of Life questionnaire (See Appendix 5.)
- VAS pain score
- VCSS (See Appendix 7.)
- Anticoagulation Review, based on the Extended Anticoagulation Protocol (See Appendix 2.)

9.9 12 Month Evaluation (365 days ± 60 days)

Patients that refuse the venogram and IVUS at this visit should have all other assessments listed here performed:

- Physical examination (to assess for the presence of Adverse Events)
- Assessment of primary patency by venography

STE-HUM-007P US Clinical Protocol Revision C

- Determination of residual external venous segment compression, stent recoil, and lesion coverage by IVUS
- Duplex ultrasound for all patients (For patients refusing the venographic assessment at this visit, DUS-determined patency will be used towards the primary efficacy endpoint instead.)
- Assessment of stent integrity by bi-plane X-Ray (See Appendix 3.)
- CIVIQ-2 Quality of Life questionnaire (See Appendix 5.)
- VAS pain score (See Appendix 6.)
- VCSS (See Appendix 7.)
- Anticoagulation Review, based on the Extended Anticoagulation Protocol (See Appendix 2.)

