15.3.1 Sensitivity Analyses: Worst-case and Tipping point

Supportive, sensitivity analyses will be performed to assess the impact of missing endpoint data. In the worst-case analysis, subjects with missing primary endpoints will be analyzed as failures with regard to that endpoint. For the primary efficacy endpoint, patients with missing data will be treated as clinical failures, i.e., re-stenosed or occluded stents. For the tipping-point analysis, the number of subjects with missing data required to be failures in order to reverse the trial conclusion will be determined.

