15.7 Primary Efficacy Endpoint

The minimum required sample size was determined using a Monte Carlo power simulation, conducted in R, testing the following hypothesis:

$$\begin{aligned} &\mathsf{H}_{\mathsf{0}}: q_{NT} * (p_{NT} - PG_{NT}) + q_{PT} * (p_{PT} - PG_{PT}) \leq 0 \\ &\mathsf{H}_{\mathsf{A}}: q_{NT} * (p_{NT} - PG_{NT}) + q_{PT} * (p_{PT} - PG_{PT}) > 0, \end{aligned}$$

where p_{NT} and p_{PT} are the observed 12-month patency rates for NT and PT subjects, respectively; PG_{NT} and PG_{PT} are pre-specified fixed performance goals for NT and PT subjects, respectively; and q_{NT} and q_{PT} , both are fixed weights for NT subjects (0.26) and PT subjects (0.74), respectively. The sample weights will not be adjusted based on actual enrollment rates.

The literature-based patency rate for the PT population is assumed to be 0.779, with corresponding performance goal (PG_{PT}) of 0.779 – 0.10 = 0.679. The literature-based patency rate for the NT population is assumed to be 0.955, with corresponding performance goal (PG_{NT}) of 0.955 – 0.10 = 0.855. Sample size is calculated to achieve at least 85% power at the one-sided 2.5% significance level:

STE-HUM-007P US Clinical Protocol Revision C

Characteristic	Value
Performance Goal	$PG_{PT} = 0.679; PG_{NT} = 0.855$
Confidence level α	0.025, one-sided
Power 1-β	≥85%
Estimated Vici patency rates	p_{PT} T = 0.779; p_{NT} = 0.955
RESULT: Sample Size	156 evaluable subjects

The estimated power is 84% for the primary efficacy endpoint (Patients who have a non-patent lesion prior to 12 months can be included in the analysis whether or not they are still being followed at 12 months because the 12-month patency status of their lesion is known).

In addition to rejecting the above hypothesis, overall success of the trial will also be determined based on whether a) the observed patency rate in the PT group is greater than 0.679, AND b) the *observed* patency rate in the NT group is greater than 0.855.

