15.8.3 Secondary Efficacy Endpoint

In order to control the overall type I error rate, the formal secondary efficacy endpoint will only be assessed if the primary endpoint objective is met. The secondary efficacy endpoint is a binary response variable based on achieving at least 50% improvement in VCSS. The following hypothesis test will be evaluated under a one-sample, one-sided exact binomial test at the 0.025 significance level:

H₀: P_{Vici} ≤ 0.50

 $H_A: P_{Vici} > 0.50,$

where $\mathsf{P}_{\mathsf{Vici}}$ is the VCSS success rate, and 0.50 is the pre-specified performance goal.

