15.9 Evaluation of Ancillary Endpoints

General Considerations

None of the evaluations of ancillary endpoints will include hypothesis tests. Instead, the mean or proportion of each will be estimated along with the 95% confidence interval (CI). Only the PP analysis will be performed on secondary endpoints (i.e., patients or limbs who contribute data will be included; those without data on a particular endpoint will be ignored).

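### Section 9.10 lets sites omit the 12-month VCSS after an early re-intervention or in-stent stenosis above 50%, and Section 15.8.3 does not say how the formal VCSS test treats those patients

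*Combined protocol and SAP*

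**What the plan says.** The formal secondary endpoint (Sections 7.3 and 15.8.3) is a VCSS improvement of at least 50% at 12 months. It is tested against 50% with a one-sided exact binomial test at 0.025. It is gated: "the formal secondary efficacy endpoint will only be assessed if the primary endpoint objective is met".

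Section 9.10 governs patients seen between visits. Those with another intervention before 12 months, or with in-stent stenosis above 50% by Core Laboratory, are primary failures and "will not be required to have further assessment of vessel patency or other secondary endpoints". A neighbouring sentence says "Patients who are found to be patent by Core Laboratory analysis will continue in the study through 12 months". The schedule in Section 10 lists no VCSS at the interval evaluation.

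Other rules bear on the same patients:

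- **Venogram refusers (Section 9.9):** "Patients that refuse the venogram and IVUS at this visit should have all other assessments listed here performed". That list includes VCSS.
- **Early failures in the patency analysis (Section 15.7):** they "can be included in the analysis whether or not they are still being followed at 12 months". Section 15.8.1 assigns them failure status.
- **Worst-case rule (Section 15.3.1):** it is limited to primary endpoints: "subjects with missing primary endpoints will be analyzed as failures with regard to that endpoint".
- **Missing secondary data (Section 15.9, on ancillary endpoints):** "those without data on a particular endpoint will be ignored".

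Section 15.8.3 itself gives the gate, the responder definition and the test. It names no analysis set and no rule for missing VCSS.

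**The concern.** A patient with a known early device failure can count in one formal test and be absent from the other, with no protocol deviation. The primary test keeps that patient. The VCSS test loses the patient if the site uses the waiver. A patient who merely declines the 12-month venogram must still be scored, so the relaxation applies to the group selected by a poor outcome.

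VCSS is the only clinical-benefit endpoint with a hypothesis test, because Section 15.9 excludes tests on ancillary endpoints. If released patients respond less often than the rest, dropping them raises the responder rate. Lower response is plausible. Interval evaluations are prompted by symptoms, and between discharge and 12 months protocol ultrasound is required only in the first 30 patients, so early failures among pivotal patients will surface mainly through symptoms. A 6-month VCSS will exist for many later failures, but the plan gives it no role in this test. A 12-month score that was never taken cannot be recovered.

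**Working it through.** **Inputs from the documents.** Null rate 0.50, assumed rate 0.62, one-sided alpha 0.025, at least 156 evaluable, power above 80% (Section 15.7.2); 170 pivotal patients (Section 8); patency 0.779 PT and 0.955 NT, weights 0.74 and 0.26 (Section 15.7).

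**Assumptions.** The documents give neither the share released before 12 months (e) nor the VCSS response of those patients (r). Both are varied. Every released patient is taken as unassessed, and all figures are conditional on the primary objective being met.

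**1. The plan's own figure.** The critical count is the smallest c with P(X ≥ c | n, 0.50) ≤ 0.025. For n = 156, c = 91, the exact size is 0.0225 and power at 0.62 is 84.7%. This agrees with the stated power.

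**2. A ceiling for e.** The planned patency rates imply a failure share of 0.74 × 0.221 + 0.26 × 0.045 = 17.5%. Some failures will first be found at the 12-month imaging, so under those rates this is an upper bound. The values 5% and 10% lie below it.

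**3. Rejection when the true overall rate is exactly 50%.** The rate among those assessed is p = (0.50 − e·r)/(1 − e). At r = 0.20 this gives (0.50 − 0.01)/0.95 = 0.516 for e = 5%, and (0.50 − 0.02)/0.90 = 0.533 for e = 10%. The response rate is overstated by 1.6 and 3.3 points.

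| Released from 156 | Assessed | c | r = 0 | r = 0.20 | r = 0.40 | r = 0.50 | r = 0.60 |
|---|---|---|---|---|---|---|---|
| 5% | 148 | 87 | 7.8% | 4.7% | 2.7% | 2.0% | 1.4% |
| 10% | 140 | 83 | 21% | 9.2% | 3.2% | 1.7% | 0.9% |

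Rejection is at or below 2.5% once r reaches about 42% (5% released) or 44% (10% released). With 2.5% released (152 assessed) and r = 0.20 it is 3.3%.

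**4. The same from 170 implanted with no other loss.** The assessed numbers are 162 and 153, with critical counts 94 and 90. At r = 0.20, rejection is 5.9% and 10%. Complete-case power at 0.62 is 87% and 81%. From 156 it is 81% (n = 148) and 77% (n = 140), but those two figures hold only if the 14 spare patients (170 − 156) are lost for other reasons.

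**5. What a just-significant result would hide.** A result of 87/148 would also be significant in all 156 only if at least 91 − 87 = 4 of the 8 released were responders. A result of 83/140 needs 91 − 83 = 8 of 16.

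**6. The gate.** With 115 PT and 41 NT (assumed from the weights) at the planned patency rates, the weighted Z-test passes with probability about 0.87. If passing were independent of VCSS, 4.7% and 9.2% become 0.869 × 0.047 = 4.1% and 0.869 × 0.092 = 8.0%.

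**7. Power when all 156 are scored.** If 62% is the overall rate, power is 84.7%. If 62% holds only among patients who would be assessed under the waiver, the overall rate is 0.62(1 − e) + e·r:

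- e = 5%, r from 0.20 to 0.50: rate 0.599 to 0.614, power 69% to 81%.
- e = 10%, r from 0.20 to 0.50: rate 0.578 to 0.608, power 48% to 76%.

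**The case against.** Several points on the other side stand.

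- **Not required does not mean not done.** Section 9.9 lists VCSS for the 12-month visit, and sites may collect it. A reader might infer that the plan excludes early failures from the VCSS test. It does not; it allows them to be missing.
- **Direction.** A reader might infer that the VCSS result will be inflated. The documents do not support that. Some released patients will have been re-treated and may score well at 12 months, and no passage gives their response. At 50% response or above there is no inflation.
- **Who is released.** A reader might take the waiver to cover every early patency failure. Section 1 defines in-stent stenosis as non-occlusive and lists thrombosis separately, so an occlusion left untreated is not named in the waiver sentence. Its release is only implied by the sentence that patent patients continue.
- **Power.** A reader might infer that the stated 80% is lost. Step 4 shows that it is kept if the 14 spare patients are available. The inflation at low response remains.
- **Other text.** Section 15.3 says that available data on dropouts will be included, which runs against discarding a VCSS that was taken. It stands under the primary analysis and cannot supply a score that was never taken. The Section 15.9 sentence sits under ancillary endpoints, so its reach to the formal test is unclear. If it applies, patients without VCSS are ignored; if not, the formal test has no rule.
- **Reach.** The VCSS test is gated, so none of this can alter the primary efficacy or safety result.

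**Conclusion.** The concern holds as a specification gap that should be fixed. A stated rule lets 12-month VCSS be missing because of a known device failure, and the formal test has no rule for the resulting gap. Confidence is high for the text and limited for the effect. Depending on the base (156 or 170), chance rejection at a true 50% rate is roughly 5% to 6% with 5% released and 9% to 10% with 10% released, if those patients respond at 20%. From 156, it stays within 2.5% if they respond at about 42% to 44% or more. These figures rest on the assumed share and response, on every released patient being unassessed, and on the primary objective being met.

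Who is released is itself unclear. Section 9.10 says that patients re-treated but found by the Core Laboratory "to have vessel patency prior to the re-intervention will not be counted as a primary efficacy endpoint failure", and then counts anyone with another intervention before 12 months as a failure.

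**What to change.** 1. **Section 9.10, waiver.** Delete the part of the waiver that concerns secondary endpoints. State that all implanted pivotal patients, whatever their patency status (stenosis, occlusion or re-intervention), remain in follow-up for the 12-month VCSS and CIVIQ-2. Amend the sentence on patent patients continuing to match; otherwise a site could still read it as releasing the others.
2. **Section 15.8.3.** State that the observed 12-month VCSS is used regardless of patency failure or re-intervention. Define the main-analysis denominator as all implanted pivotal patients with a 12-month VCSS, and report the number and patency status of those missing. Add worst-case (missing counted as non-responder) and tipping-point analyses for VCSS. Make Section 15.9 consistent.
3. **Section 9.10, re-intervention.** Reconcile the two statements on re-intervention with a patent vessel.

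Counting early failures without VCSS as non-responders in the main analysis is an option, but it mixes patency into a clinical endpoint and is not needed here.

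The cost is wording in three sections, plus a short clinician score and a questionnaire at an already scheduled visit in a few patients. The VCSS response rate and power may also be lower if released patients respond less often, over the range in step 7 of the working.
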